	
Technical Success, Repeat Ablation Efficacy, and Hospital Readmission Rate will be summarized in a similar manner. Local Tumor Progression, Local Tumor Progression Free Survival, Progression Free Survival, and Overall Survival will be estimated using the Kaplan-Meier method and confidence intervals will be provided.
 
The number and percentage of subjects experiencing device-related AEs will be summarized by the MedDRA system organ class and preferred term. A similar summary will also be provided for procedure-related AEs and all SAEs.
 
Summary statistics will be provided for all other endpoints as defined within the protocol.

Interim Analyses	
The first interim analysis will occur after 20 subjects complete Visit 3 (30 days) and will be descriptive in nature only and will not impact the final analysis.
 
The second interim analysis will occur after all subjects complete Visit 3 (30 days) and will include an evaluation of the primary endpoint against the performance goal as well as provide a summary of all baseline and procedural-related data. A complete summary of all safety-related data observed through the duration of follow-up on all subjects will also be provided. The intent of this analysis will be to support regulatory filing activities where appropriate.
 
An additional interim analysis may be performed after all subjects have completed Visit 5 (6 months).
 
The final analysis will be completed once all subjects have completed Visit 6 (12 months) and will summarize all endpoints collected during the trial.

Time and Events Schedule	See Table 1 on the next page.

Table 1: Schedule of Assessments

Visit No.	Visit 1	Visit 2			Visit 3	Visit 4	Visit 5	Visit 6	Unsched. Visit ²¹
Visit	Screening	Pre-Procedure	Intra-Procedure	Post-Procedure	Follow-up	Follow-up	Follow-up	Follow-up	
Interval Windows	≤ 30 days pre-ablation	Day 0	Day 0	Day 0 - Discharge	30 days (-7 to +14 days)	3 months (±2 weeks)	6 months (±1 month)	12 months (±1 month)	
Standard Study Assessments									
Informed Consent	X								
Inclusion / Exclusion Criteria	X	X							
Demographics	X								
Medical / Surgical History ¹	X								
Concomitant medications ²	X	X		X	X	X	X	X	X
Concomitant procedures	X	X		X	X	X	X	X	X
BMI	X								
Key Vitals ³	X	X		X	X	X	X	X	
ECOG Status	X	X			X	X	X	X	
Pulmonary function tests (PFTs)	X					X	X	X	
Laboratory Assessments									
Pregnancy test ⁴	X	X							
Coagulation tests ⁵	X	X ⁶							
CBC with differential	X								

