10.8 Sample Size Justification

10.9 Analyses to be Conducted

Analyses described below will be performed on all enrolled and ablated subjects.

Disposition of Study Subjects

Subject disposition will be summarized using counts and percentages. The number and percentage of subjects completed and discontinued along with the specific reasons for discontinuation will be tabulated by ablation group and in total.

Demographic and Baseline Characteristics

Summary statistics will be provided for subject demographics and pre-operative ablation characteristics.

Primary and Secondary Endpoint Analyses

The number and percentage of tumors achieving Technique Efficacy will be summarized and a 95% confidence interval will be estimated. Hypothesis testing for the primary endpoint will be performed using the methodology described in the previous section. The number and percentage of tumors achieving Technical Success will also be summarized, and a 95% confidence interval will be estimated. Local Tumor Progression will be summarized in a similar manner. Only target lesions will be included in the primary endpoint analysis for Technique Efficacy and primary summaries of Technical Success and local Tumor Progression. Data collected on non-target tumors for these endpoints will be summarized separately and not included as part of the primary analysis. The analysis of target tumors for these three endpoints will also include a subject level summary that will be secondary or supportive to the tumor level analysis.

Summary statistics will be provided for other secondary endpoints, as appropriate, for continuous or categorical variables. Local Tumor Progression Free Survival, Progression Free Survival, and Overall Survival will be estimated using the Kaplan-Meier method and confidence intervals will be provided.

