#### 8.8.2 Secondary Endpoints and associated hypotheses

##### **Technical Success and Local Tumor Progression:**

Technical Success is defined as: All A0 and A1 ablation classification determinations (complete tumor ablation with a surrounding minimal margin) as assessed by cone beam CT (CBCT) imaging, immediately following the ablation procedure. (Note: A0 = Complete tumor ablation with an ideal minimal margin, i.e., a surrounding minimal margin of at least 5mm. A1 = Complete tumor ablation with a minimal margin, i.e., a surrounding minimal margin of less than 5mm but more than 0mm.)

Local Tumor Progression (LTP) is defined as: Recurrence of originally ablated target tumor(s) within or abutting the ablation zone using 30-day post-ablation imaging as the baseline.

The number and percentage of target tumors achieving Technical Success will be summarized. Local Tumor Progression (target tumors only) will be summarized in a similar manner.

Data collected on non-target tumors for these endpoints will be summarized separately. In addition, Technique Efficacy, Technical Success, and Local Tumor Progression results will be include a subject level summary in addition to the tumor level analysis.

Detail regarding new or recurrent lung tumors post procedure will be summarized similarly to the pre-ablation, such as target/non-target, location, size, and distance from pleura.

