**Time to Event Endpoints:**

Local Tumor Progression Free Survival (LTPFS) is defined as: Time from the ablation until local tumor(s) progression (LTP) or death, whichever occurs first.

Progression Free Survival (PFS) is defined as: Time from the original ablation until tumor(s) progression or death, whichever occurs first (includes local, regional, or distant progression). Specifically: For local tumors, time from the original ablation until tumor(s) progression or death, whichever occurs first. For regional and distant tumors, time from study day 0 or last local therapy (if treated after study initiation) until tumor(s) progression or death, whichever occurs first.

Disease (cancer) Specific Survival (DSS) is defined as: Time from the original ablation until death from the treated primary malignancy.

Overall Survival (OS) is defined as: Time from the original ablation until subject death (includes death from any cause).

Local Tumor Progression Free Survival (LTPFS), Progression Free Survival (PFS), Disease Specific Survival (DSS), and Overall Survival (OS) will be estimated using the Kaplan-Meier method with 95% confidence intervals provided at month 12. The time from the day of the initiation ablation procedure to the specific event will be derived.

Patients who are re-ablated are considered as reaching an event respectively for each of the LTP, LTPFS and PFS event definitions.

Patients without a progression event, as defined above, will be censored by the last contact date (the last date in the study).

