### **8.13 Handling of Missing Data**

No imputation will be used for missing data or early dropouts in all analysis except in the sensitivity analyses for the primary endpoint (see Section 8.8.1). Time-to-event analyses will use standard censoring assumptions for the handling of subjects who do not have event or do not complete follow-up visits (see Section 8.8.2).

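### Local Tumor Progression is assigned to Kaplan-Meier in the Protocol Summary but to a percentage with no stated denominator or time point in Protocol 10.9 and SAP 8.8.2; under dropout that percentage is biased in a direction set by the denominator

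*SAP*

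**What the plan says.** Three places describe how LTP will be analysed.

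- **Protocol 1.0, Protocol Summary, Statistical Analyses:** "Local Tumor Progression, Local Tumor Progression Free Survival, Progression Free Survival, and Overall Survival will be estimated using the Kaplan-Meier method", with confidence intervals.
- **Protocol 10.9:** "Local Tumor Progression will be summarized in a similar manner". The sentence before it supplies the manner: "The number and percentage of tumors achieving Technical Success will also be summarized, and a 95% confidence interval will be estimated". The Kaplan-Meier sentence in the same section leaves LTP out: "Local Tumor Progression Free Survival, Progression Free Survival, and Overall Survival will be estimated using the Kaplan-Meier method".
- **SAP 8.8.2, Technical Success and Local Tumor Progression:** "Local Tumor Progression (target tumors only) will be summarized in a similar manner", again following Technical Success. Here it is a number and percentage, and no interval is mentioned. A subject-level summary accompanies the tumor-level one.

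The Kaplan-Meier list in SAP 8.8.2, Time to Event Endpoints, covers Local Tumor Progression Free Survival (LTPFS), progression-free, disease-specific and overall survival. These "will be estimated using the Kaplan-Meier method with 95% confidence intervals provided at month 12". LTP is not listed, yet the same subsection gives it an event rule: "Patients who are re-ablated are considered as reaching an event respectively for each of the LTP, LTPFS and PFS event definitions". A censoring rule at last contact follows for patients without a progression event.

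SAP 8.13 adds: "No imputation will be used for missing data or early dropouts in all analysis except in the sensitivity analyses for the primary endpoint".

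**The concern.** Technical Success is read once, straight after ablation, so a percentage of treated tumors suits it. LTP is read at Visits 4, 5 and 6 (3, 6 and 12 months), with the 30-day scan as baseline. A subject who leaves after month 3 has an unknown LTP status at month 12. A percentage has to count that tumor as free of progression or leave it out, and neither document says which.

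LTPFS does not fill the gap. It handles censoring, but it counts every death as an event, so it does not isolate local failure.

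What is at stake is the reported rate of local failure after day 30. The documents name Kaplan-Meier in one place and a percentage in two, and the percentage has at least two possible denominators. In an open-label study the choice could be made after the data are known.

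**Working it through.** **The plan's own figures.** The documents give no expected rate, precision or power for LTP. Their only sample size (137, or 145 with 5% dropout) is for Technique Efficacy at 30 days. It reproduces: ((1.960×√(0.80×0.20) + 1.282×√(0.90×0.10))/0.10)² = 136.5, so 137; 137/0.95 = 144.2, so 145. It has no bearing on LTP.

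**Inputs.**
- Scan times 3, 6 and 12 months: schedule of assessments in both documents.
- True 12-month LTP of 15%: an assumption. Protocol 3.0 cites local control above 85% for percutaneous ablation, with no time point. Values of 10% and 20% are also tried.
- Dropout of 10%, 20% and 30% by month 12: assumptions. SAP 7 allows 5% at 30 days and gives no 12-month rate.
- Constant hazards, non-informative dropout, one target tumor per subject.

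**Formulas.** With t in years, let S(t) = 0.85^t be the share free of LTP and G(t) = (1−c)^t the share still in the study, where c is 12-month dropout. LTP arising between scans a and b is seen only if the subject attends scan b.

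- Detected share of all target tumors: D = Σ [S(a) − S(b)] × G(b), over the intervals 0–3, 3–6 and 6–12 months.
- Share of evaluable tumors (detected LTP, or followed free of LTP to month 12): D / (D + S(1)×G(1)).

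**Worked case, 20% dropout and no deaths.** S is 0.9602, 0.9220 and 0.8500, so the drops are 0.0398, 0.0382 and 0.0720. G is 0.9457, 0.8944 and 0.8000.

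- D = 0.0398×0.9457 + 0.0382×0.8944 + 0.0720×0.8000 = 0.0376 + 0.0342 + 0.0576 = 0.1294, or 12.9%.
- Evaluable: 0.1294 / (0.1294 + 0.85×0.80) = 0.1294/0.8094, or 16.0%.
- An estimator that uses the tumors actually scanned at each visit recovers 15.0%.

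| Dropout by month 12, no deaths | Over all target tumors | Over evaluable tumors | True |
|---|---|---|---|
| 10% | 14.0% | 15.5% | 15.0% |
| 20% | 12.9% | 16.0% | 15.0% |
| 30% | 11.9% | 16.6% | 15.0% |

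At 20% dropout the same pair is 8.6% and 10.7% if true LTP is 10%, and 17.3% and 21.3% if it is 20%.

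**Deaths alone.** Put 20% deaths in place of dropout. D is again 12.9%, but now it equals the cumulative incidence of detected LTP with death as a competing event. One minus Kaplan-Meier, with deaths censored, gives 15.0%, which is above that incidence.

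**Both together, 20% deaths and 20% dropout.** All-tumor percentage 11.2%; cumulative incidence 12.9%; one minus Kaplan-Meier 15.0%; evaluable-only percentage 17.1%. The spread is 17.1 − 11.2 = 5.9 points on one set of data.

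**The case against.** Much can be said for leaving this alone. LTP is one of ten secondary endpoints and carries no hypothesis test. The shift from dropout alone is small beside sampling error: at 15% in 145 tumors, one per subject, the 95% half-width is about 1.96×√(0.15×0.85/145) = 5.8 points. The loss rates are assumed. A time-to-event analysis that includes local progression is already planned through LTPFS, which SAP 5 singles out for a month-12 interval. These points stand, and they limit the weight of the finding. They do not settle which estimator applies to LTP.

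A reader might infer that the percentage always favours the device. The documents do not support that, because they state no denominator. The rule against imputation in SAP 8.13 sits awkwardly with counting a lost tumor as progression-free, and an evaluable-only denominator overstates local failure.

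A reader might also infer that deaths make the all-tumor percentage too low. Against the competing-risk incidence they do not; only dropout does. For the same reason, simply restoring the Summary's Kaplan-Meier wording is not a clean repair: with deaths censored, it exceeds the incidence that patients experience.

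Finally, nothing in either document makes LTP the trial's main measure of durable control. It is, however, the listed endpoint that isolates local failure after day 30.

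**Conclusion.** The contradiction is plain and lies in current text: Kaplan-Meier in the Protocol Summary, a percentage in Protocol 10.9 and SAP 8.8.2. The SAP also supplies an LTP event rule under its time-to-event heading without naming an estimator to use it. Giving precedence to the SAP would not resolve the matter, because the SAP leaves the denominator and time point open.

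On size, dropout biases the percentage under either denominator. At a true 15%, all-tumor figures fall short by 1.0 to 3.1 points and evaluable-only figures run over by 0.5 to 1.6 points, for dropout of 10% to 30%. This rests on constant hazards, detection at scans, non-informative dropout and assumed rates. No general direction of bias can be claimed. This is a gap in pre-specification for a descriptive secondary endpoint. It should be closed, and it does not touch the primary test.

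**What to change.** Name one estimator for LTP in the Protocol Summary, Protocol 10.9 and SAP 8.8.2:

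- cumulative incidence at 12 months per target tumor;
- death as a competing event;
- subjects without an event censored at the last evaluable chest CT, stated separately from the SAP's last-contact rule;
- a 95% interval that allows for two target tumors in one subject.

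Keep the crude number and percentage as a description, with the denominator and time point written out. Do not fall back on Kaplan-Meier with deaths censored as the sole method.

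The cost is wording in both documents and one extra standard table. No new data are needed, and the sample size and primary test are unaffected.

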**Time to Event Endpoints:**

Local Tumor Progression Free Survival (LTPFS) is defined as: Time from the ablation until local tumor(s) progression (LTP) or death, whichever occurs first.

Progression Free Survival (PFS) is defined as: Time from the original ablation until tumor(s) progression or death, whichever occurs first (includes local, regional, or distant progression). Specifically: For local tumors, time from the original ablation until tumor(s) progression or death, whichever occurs first. For regional and distant tumors, time from study day 0 or last local therapy (if treated after study initiation) until tumor(s) progression or death, whichever occurs first.

Disease (cancer) Specific Survival (DSS) is defined as: Time from the original ablation until death from the treated primary malignancy.

Overall Survival (OS) is defined as: Time from the original ablation until subject death (includes death from any cause).

Local Tumor Progression Free Survival (LTPFS), Progression Free Survival (PFS), Disease Specific Survival (DSS), and Overall Survival (OS) will be estimated using the Kaplan-Meier method with 95% confidence intervals provided at month 12. The time from the day of the initiation ablation procedure to the specific event will be derived.

Patients who are re-ablated are considered as reaching an event respectively for each of the LTP, LTPFS and PFS event definitions.

Patients without a progression event, as defined above, will be censored by the last contact date (the last date in the study).

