4.3 Secondary Endpoints

- Technical Success: All A0 and A1 ablation classification determinations (complete tumor ablation with a surrounding minimal margin) as assessed by cone beam CT imaging, immediately following the ablation procedure.
- Navigational Success: Successful navigation to the targeted peripheral lung tumor(s) as confirmed using cone beam CT (CBCT).
- Local Tumor Progression (LTP): Recurrence of originally ablated target tumor(s) within or abutting the ablation zone using 30-day post-ablation imaging as the baseline. Measuring progression details will be outlined in a separate Imaging Charter.
- Local Tumor Progression Free Survival (LTPFS): Time from the ablation until local tumor(s) progression (LTP) or death, whichever occurs first. Measuring progression details will be outlined in a separate Imaging Charter.

- Progression Free Survival: Time from the original ablation until tumor(s) progression or death, whichever occurs first (includes local, regional, or distant progression). Measuring progression details will be outlined in a separate Imaging Charter.
- Disease (cancer) Specific Survival: Time from the original ablation until death from the treated primary malignancy.
- Overall Survival: Time from the original ablation until subject death (includes death from any cause).
- Repeat Ablation Efficacy Rate: Rate of original tumors that have been re-ablated successfully (i.e., Technical Success of tumors that have been re-ablated/all original tumors that have been re-ablated).
- Change in all available PFTs (pulmonary function tests) from pre-ablation baseline values to values at 3 months, 6 months, and 12 months post-ablation.
- Change in overall health-related quality of life (HRQOL) and sub-scales, including physical functioning and pain domains, per the validated EORTC QLQ-C30 and QLQ-LC13 questionnaires throughout the duration of the study.

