## 1 Study Design

This is a prospective, multicenter, single-arm study of transbronchial microwave ablation using robotic-assisted bronchoscopy in adult subjects with oligometastatic tumors ( $\leq 2\text{cm}$ ) in the lung, located in the outer two-thirds and not closer than 1cm to the pleura (including fissures), with colorectal, renal, or sarcoma histology.

Subjects with at least one oligometastatic tumor in the lung who meet all inclusion/exclusion criteria will have transbronchial microwave ablation performed using CBCT scan for probe guidance and confirmation. Subjects will be followed for 12 months following the first ablation procedure for safety and effectiveness outcomes.

Overall, the study will include up to 145 subjects across approximately 15 sites, where principal investigators will be licensed pulmonologists/interventional pulmonologists or thoracic surgeons who have completed at least 20 diagnostic cases using the MONARCH Platform including at least 5 cases using CBCT and completed the Sponsor-required FLEX MC training.

In this study, “target” tumors are defined as lung tumors that are treated with FLEX MC at the index ablation procedure (i.e., Visit 2). A subject may have a maximum of two target tumors. “Non-target” tumors are defined as lung tumors that are treated with FLEX MC during study follow-up after completion of the primary endpoint, Technique Efficacy assessments at Visit 3 (i.e., Visits 3-6). A subject may not have more than three total tumors treated with FLEX MC (including target and non-target tumors).

A central review committee of radiologists will independently review all CT scans (and other scans, as applicable) taken throughout the clinical study in an effort to standardize scan assessment and to minimize potential bias of the treating physician. Both the clinical site’s radiographic assessment and the central review committee’s assessment will be captured within the CRFs and reported within the final Clinical Study Report. The central review committee assessment for the following key endpoints will be used for the final analysis.

Assessment	Visit 1 (Screening)	Visit 2 (Ablation Visit)	Visit 3 (30 days post-ablation)	Visit 4 (3 months post-ablation)	Visit 5 (6 months post-ablation)	Visit 6 (12 months post-ablation)
Tumor size* (smallest and largest diameters)	X					
Ablation zone (smallest and largest diameters)		X				
Smallest minimal ablation margin		X				
Technical Success		X				

Technique Efficacy			X			

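### SAP 8.8.2 gives PFS two conflicting start dates, and censors PFS and LTPFS at last contact rather than at the last tumor assessment

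*SAP*

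**What the plan says.** Protocol 4.3 gives PFS one origin: "Progression Free Survival: Time from the original ablation until tumor(s) progression or death, whichever occurs first", counting local, regional and distant progression. It leaves the measurement of progression to another document: "Measuring progression details will be outlined in a separate Imaging Charter".

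SAP 8.8.2 (Time to Event Endpoints) first repeats the protocol definition. It then splits it. Local tumors are timed from the original ablation, but "For regional and distant tumors, time from study day 0 or last local therapy (if treated after study initiation) until tumor(s) progression or death". A later sentence covers all four time-to-event endpoints: "The time from the day of the initiation ablation procedure to the specific event will be derived".

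On censoring, the same section says: "Patients without a progression event, as defined above, will be censored by the last contact date (the last date in the study"). SAP 8.13 refers back to this rule and adds none for missed scans. LTPFS, PFS, DSS and OS "will be estimated using the Kaplan-Meier method with 95% confidence intervals provided at month 12".

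On follow-up, SAP 1 states: "Subjects will be followed for 12 months following the first ablation procedure for safety and effectiveness outcomes". SAP Table 1 allows Visit 6 at 12 months ±1 month.

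**The concern.** **Origin.** Kaplan-Meier needs one time per subject. Table 1 makes the ablation visit Day 0, so study day 0 and the original ablation coincide. The real conflict is with the last-local-therapy clause. It is not an empty clause, because later local therapy is part of the design. Inclusion criterion 5 admits up to five tumors in up to three organs. Protocol 6.1 requires the multidisciplinary team to settle how and when every disease site is treated, and it allows a third lung tumor to be ablated at a later visit.

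**Censoring.** Progression is established on images. Contact can continue without them; for example, the Visit 6 questionnaires may be given by telephone. Censoring at contact treats the unscanned interval as known to be progression-free.

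**At stake.** SAP 5 names PFS and LTPFS among four endpoints that receive a 95% confidence interval at month 12 if the primary endpoint succeeds. Two programmers following the SAP could report different PFS estimates from the same data, and the censoring rule pushes PFS and LTPFS upward.

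**Working it through.** **1. The origins side by side**

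| Text | PFS clock starts at |
|---|---|
| Protocol 4.3 | original ablation |
| SAP 8.8.2, first PFS sentence | original ablation |
| SAP 8.8.2, local tumors | original ablation |
| SAP 8.8.2, regional and distant tumors | day 0, or last local therapy if later |
| SAP 8.8.2, derivation sentence | day of the initial ablation |

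Take a hypothetical subject with local therapy on day 100. Regional progression on day 183 gives a PFS time of 183 days from the ablation, or 183 − 100 = 83 days from last local therapy. Death without progression is worse defined. Both component definitions end in death, so death on day 300 gives 300 days on the local clock and 200 on the regional/distant clock.

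**2. Reach of a restarted clock.** Visit 6 is at month 13 at the latest. After a restart at month L, the longest observable time is 13 − L, which is below 12 whenever L > 1. Non-target tumors are by definition treated only after the Visit 3 assessment (30 days, −7 to +14), so most such restarts cannot reach the read-out.

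**3. Inputs for size.** The SAP gives no expected PFS rate or event count, so there is no PFS figure to reproduce.
- From the documents: 12-month PFS of 58% (Protocol 3.0, image-guided ablation), N = 145 (SAP 7), and visit windows of 3 months ±2 weeks, 6 ±1 month and 12 ±1 month.
- N itself reproduces: [(1.96·√0.16 + 1.2816·√0.09)/0.10]² = 136.5, so 137; 137/0.95 = 144.2, so 145.
- Assumed: independent exponential progression and death; 12-month OS of 92%; visits uniform within their windows; progression found at the next scheduled scan; and the restart and missed-scan shares below.

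Sampling error for comparison: 1.96·√(0.58·0.42/145) = 0.080, a half-width of about 8 points.

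**4. Effect of the restart.** The restart applies to subjects still event-free at local therapy in months 1-3, and L is subtracted from their event or censoring time. Times are at nominal visits.

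| Share restarted | 12-month PFS | Change from 58.3% | At risk at month 12 (of 145) |
|---|---|---|---|
| 0% | 58.3% | – | 106 |
| 10% | 57.0% | −1.3 | 96 |
| 20% | 55.6% | −2.7 | 85 |
| 30% | 54.0% | −4.3 | 74 |

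Other dating readings and therapy at months 1.5-4 give −1.2 to −4.8. A simpler run, with exact event dates and a restart at days 14-90, gives only −0.5, −0.9 and −1.3 points for the same shares. The direction is the same throughout: the restart discards event-free time before the later therapy and keeps every event after it.

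**5. Effect of last-contact censoring.** The same simulated data are analysed under both rules, with a share of subjects contacted but unscanned at Visit 6.

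| Unscanned | Actual dates: contact / scan | Difference | Nominal visits: contact / scan | Difference |
|---|---|---|---|---|
| 5% | 64.3 / 63.6 | +0.7 | 58.9 / 58.0 | +0.9 |
| 10% | 64.8 / 63.2 | +1.6 | 59.6 / 57.8 | +1.8 |
| 20% | 65.7 / 62.4 | +3.3 | 61.1 / 57.5 | +3.6 |

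A separate simulation on actual dates gives 66.2 − 64.7 = +1.5 at 10% and 67.2 − 64.1 = +3.1 at 20%. For LTPFS (true rate assumed 85%), the differences are +0.3, +0.7 and +1.5 points. If nobody misses the scan, the two rules agree.

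**The case against.** **The regional/distant clause may be a deliberate refinement.** Timing a tumor from its own treatment is sensible when that treatment was planned from the start. Even so, the SAP does not say how the two clocks combine into one time per subject, the derivation sentence contradicts the clause, and the protocol does not contain it.

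**The effects are small and every rate is assumed.** This stands. The documents give no rate for later local therapy or for missed Visit 6 scans, and PFS and LTPFS carry no test or performance goal. The 58% and 60% in Protocol 3.0 are background, not a comparator. LTP is also reported as a simple percentage.

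**Stronger readings that the documents do not support.**
- A reader might infer that month 12 is undefined and that the estimate is wrong for that reason. Time derived from the ablation day, with no added analysis windows (SAP 4), reads naturally as actual elapsed time. The gap between the 58% true rate and the roughly 64% on actual dates is the ordinary detection lag of scheduled imaging. The Imaging Charter, which was not available, may fix how progression is dated.
- A reader might infer that re-ablation of a target tumor restarts the clock. It does not: "Patients who are re-ablated are considered as reaching an event respectively for each of the LTP, LTPFS and PFS event definitions". A new lung tumor likewise already counts as regional progression. The clear cases for a restart are a planned third lung tumor and planned treatment of other sites.
- A reader might infer that last-contact censoring is wrong for all four endpoints. It is suitable for OS and DSS, which do not depend on scans.

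**Conclusion.** Both faults hold on the text. The PFS origin is contradictory within one SAP section and against Protocol 4.3, so PFS is not uniquely defined for subjects with later planned local therapy. Last-contact censoring biases PFS and LTPFS upward whenever contact outlasts imaging.

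Under the assumptions above, a restart in 10-30% of subjects lowers 12-month PFS by about 1 to 4.5 points, or 0.5 to 1.3 with early restarts and exact event dates. Last-contact censoring raises it by about 1.5 to 3.5 points if 10-20% are unscanned. The two pull in opposite directions, and each is below the 8-point half-width. The primary endpoint, its significance level and the sample size are untouched. The point should be corrected before database lock, chiefly so that the definition is not chosen after the data are seen. It does not threaten the trial's main conclusion.

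**What to change.** In SAP 8.8.2:
1. Delete the last-local-therapy origin, so that PFS runs from the original ablation to first local, regional or distant progression or death, as in Protocol 4.3.
2. Censor PFS and LTPFS non-progressors at the last evaluable imaging assessment. Keep last contact, or date last known alive, for OS and DSS.

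Optional: because Visit 6 spans months 11-13, add an interval-censored (Turnbull) estimate as a sensitivity analysis, or cite the Imaging Charter's dating rule if it has one. If nominal visit dates are used, apply them to both progression and censoring times. Moving only the progression dates leaves censored subjects dropping out between months 11 and 12 while progressors from the same scans stay at risk. In simulation this gives about 47-48% for a true 58%, roughly 10 points too low.

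The cost is SAP wording and programming, with no new data. The first change may raise reported PFS slightly; the second may lower PFS and LTPFS slightly.
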